7.3 Concomitant Medication, Drug-Drug interactions and Procedures

Participants in sub-study 3 must be instructed not to take any medications, except tylenol, including over the counter products such as NSAIDs, without first consulting with the investigator. Participants in sub-study 1 must be instructed not to take any medications, including Tylenol and over the counter products such as NSAIDs, without first consulting with the investigator.

Drug Interactions

The following medicines are allowed but should be carefully monitored.

Digoxin: Concomitant HCQ and digoxin therapy may result in increased serum digoxin levels.

Insulin or antidiabetic drugs: As HCQ may mildly enhance the effects of a hypoglycemic treatment, a decrease in doses of insulin or antidiabetic drugs may be required.

Drugs that prolong QT interval and other arrhythmogenic drugs: HCQ can prolong the QT interval and should not be administered with other drugs that have the potential to induce cardiac arrhythmias. Also, there may be an increased risk of inducing ventricular arrhythmias if HCQ is used concomitantly with other arrhythmogenic drugs. A full list of these drugs can be found at <https://crediblemed.org>

Antiepileptics: The activity of antiepileptic drugs might be impaired if co-administered with HCQ.

The PATCH Trial

Cyclosporin: An increased plasma cyclosporin level was reported when cyclosporin and HCQ were co-administered.

Because HCQ has known effects on P450 enzymes, patients requiring anti-convulsants may be treated with any of the non-enzyme inducing anti-convulsants which include: felbamate, valproic acid, gabapentin, lamotrigine, tiagabine, topiramate, or levetiracetam. Due to the fact that both zonisamide and HCQ accumulate in red blood cells, zonisamide should be avoided if possible. All other concomitant medications are permitted.

The following medications are not allowed during the study. The sponsor must be notified if the subject receives any of these during the study:

1. Sub-study 1: Any investigational or off-label antiviral therapy
2. Immunosuppressive medications, including, corticosteroids at doses exceeding 10mg/day of prednisone or equivalent, methotrexate, azathioprine, and TNF-alpha blockers. Use of immunosuppressive medication for the management of study treatment-related AEs or in subjects with contrast allergies is acceptable. In addition, use of topical, inhaled and intranasal corticosteroids is permitted

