Clinical Symptom monitoring: Appropriately delegated and credentialed study team members (as example: CRC) will screen for symptoms 1X per week and if present will document the likely treatment related AEs. Follow up with an appropriately delegated and credentialed physician investigator will be undertaken for assessment and grading of events. Participants will be asked if there have been changes in vision such as distortions of blurred vision. Patients who develop COVID-19 symptoms will be instructed to go to occupational health for nasopharyngeal swab. The rate of conversion to PCR positive in each arm at the 2-month mark will be used to assess the primary endpoint.

Electrocardiogram Recordings: An electrocardiogram (12 lead or 6 lead) will be recorded at baseline prior to the initiation of the study drug. Those participants with an ECG in the last 6 months and no QTc prolonging medications do not need a repeat baseline ECG. One month after starting the study drug a repeat ECG will be performed to confirm excessive QTc prolongation has not occurred. If the QTc has prolonged to >500ms dose reduction as described below will be attempted to achieve a QTc of <500ms. Due to the long half-life of HCQ, study medication can be started before the baseline ECG is read.

Pill diary: Electronic pill diary will be turned in by the participant at the end of the study.

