Oral fluid collection: Participants will be asked to collect oral fluid using the RNAPro-Sal collection kit manufactured by Oasis Diagnostics (<https://4saliva.com/products/rnapro-sal/>). These kits will be provided to the participant with the drug supply. The participant will have clear instructions on how to collect oral fluid on themselves. This process consists of inserting the gauze tip in the mouth for 4 minutes, removing and pushing the syringe to squeeze the fluid into the container. A video will be sent to the participant's email address and texted to them providing visual instructions on use. Participants should produce an early morning saliva sample from the posterior oropharynx (ie, coughed up by clearing the throat) before tooth brushing and breakfast, because nasopharyngeal secretions move posteriorly and bronchopulmonary secretions move by ciliary activity to the posterior oropharyngeal area while the patients are in a supine position during sleep. Participants will be instructed to collect oral fluid at the following time-points in the containers provided (before taking the first dose of study and every 2 weeks after that). The collected oral fluid should be placed in the freezer in a sealed container. This container will be collected after the participant is at the end of their participation. The participant will then wipe the container surface with disinfectant and return to site. If the participant becomes quarantined or hospitalized with COVID-19, a primary contact for the participant will be contacted and if asymptomatic and/or COVID-19 negative the driver will pick up the saliva using the same procedure.

8.5 Hydroxychloroquine Dose Reduction.

In outpatient arms 1 and 3, any AE of \geq Grade 2 or adjusted QTc prolongation to >500ms and attributed as possibly, probably or definitely related solely to HCQ will result in dose holiday and/or dose reduction of HCQ as described in Table 5. No more than 1 dose reductions are allowed.

Table 3: Hydroxychloroquine Dose Reduction Schema

Sub-Study	Dose mg/day	First dose reduction
1	400 mg twice daily	400mg daily
3	600 mg daily	400 mg daily

- If the second dose reduction is not tolerated, then the patient should discontinue the treatment.

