11.2.1 Relationship to study drug: Yes

There is a plausible temporal relationship between the onset of the AE and administration of the study drug, and the AE cannot be readily explained by the participant's clinical state, intercurrent illness, or concomitant therapies; and/or the AE follows a known pattern of response to the study drug; and/or the AE abates or resolves upon discontinuation of the study drug or dose reduction and, if applicable, reappears upon re-challenge.

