11.2.2 Relationship to study drug: No

Evidence exists that the AE has an etiology other than the study drug (e.g., preexisting medical condition, underlying disease, intercurrent illness, or concomitant medication); and/or the AE has no plausible temporal relationship to study drug administration (e.g., cancer diagnosed 2 days after first dose of study drug).

Expected adverse events are those adverse events that are listed or characterized in the Package Insert.

Unexpected adverse events are those not listed in the Package Insert. This includes adverse events for which the specificity or severity is not consistent with the description in the Package Insert. For example, under this definition, hepatic necrosis would be unexpected if the Package Insert only referred to elevated hepatic enzymes or hepatitis.

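### Sub-study 3: 8.4.2 asks for dose reduction at any one-month QTc above 500 ms, but the dose rule it points to (8.5) ties the QTc trigger to attribution solely to HCQ

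*Protocol*

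**What the plan says.** Three parts of the protocol bear on a long QTc in sub-study 3.

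- **Section 8.4.2, electrocardiogram paragraph.** It gives the purpose of the on-treatment reading: "One month after starting the study drug a repeat ECG will be performed to confirm excessive QTc prolongation has not occurred". It then gives the action: "If the QTc has prolonged to >500ms dose reduction as described below will be attempted to achieve a QTc of <500ms". No causality condition is attached.
- **Section 8.5, the dose rule for sub-studies 1 and 3.** It names two triggers, an adverse event of grade 2 or higher and a long QTc, followed by an attribution clause: "adjusted QTc prolongation to >500ms and attributed as possibly, probably or definitely related solely to HCQ will result in dose holiday" and/or dose reduction. One step down is allowed; in sub-study 3 this is from 600 mg to 400 mg daily.
- **Section 8.4.1, the parallel rule for sub-study 1.** Dose is adjusted when needed to bring adjusted QTc below 500 ms. This passage also states no attribution test.

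Section 5.0 says that only the pharmacist knows the assignment. The staff who would judge attribution to HCQ therefore do not know whether the participant is taking it.

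**The concern.** The schedule of events for sub-study 3 has a single on-treatment ECG, at one month, and a footnote to Table 6 lets it be deferred. The rule for acting on that one reading should leave no doubt.

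As written, the threshold is the same in both sections but the condition is not. If a participant has QTc above 500 ms and another possible cause, 8.4.2 asks for a reduction. A reader who treats 8.5 as the operative dose rule may conclude that its trigger has not been met. What is at stake is how a recognised cardiac risk of the study drug is handled in healthy volunteers. The efficacy comparison is not at stake.

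**Working it through.** The main check is a comparison of texts. The plan gives no figure to reproduce.

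**1. Does the attribution clause reach the QTc trigger?** It follows directly after the QTc words. Whether it modifies both triggers or only the nearer one, it covers QTc. To confine it to adverse events, it would have to skip its nearest antecedent. As history only, the dose-reduction section of the original protocol carried the clause with the adverse event trigger alone, and Amendment 1 added QTc. That may explain the wording but does not settle its meaning.

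**2. What does the pointer in 8.4.2 bring in?** The dose-reduction text below it is 8.5. The pointer could import the whole rule, including the condition, or only the dose steps. Nothing in the protocol or SAP says which.

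**3. Can the condition be applied?** The only relationship scale defined, in 11.2.1 and 11.2.2, is Yes or No. It has no possible, probable or definite grades and no sole-cause category. A long QTc in someone also taking another QT-prolonging drug can meet Yes through "the AE follows a known pattern of response to the study drug", and can also meet No through "Evidence exists that the AE has an etiology other than the study drug".

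**4. Is a second cause foreseeable?** Yes, but it is partly controlled. Section 7.3 places QT-prolonging drugs under the heading "The following medicines are allowed but should be carefully monitored", and then says "HCQ can prolong the QT interval and should not be administered with other drugs that have the potential to induce cardiac arrhythmias". Sub-study 3 participants "must be instructed not to take any medications, except tylenol" without consulting the investigator. Section 3.2 excludes seven named QT-prolonging drugs and several cardiac conditions. It sets no QTc limit for entry, and 8.4.2 lets drug start before the baseline ECG is read.

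**5. What would be the dose difference for one affected person?** Inputs: eight weeks of drug (SAP, Study Design), ECG at week 4, and 600 mg or 400 mg daily (8.5). Days left = 56 − 28 = 28. The holiday lengths are assumptions, taken from the 7-day limit in 10.3 and the 14-day limit in 8.2.

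| Course after the ECG | Total dose | Less than staying on 600 mg |
|---|---|---|
| 600 mg daily | 28 × 0.6 = 16.8 g | 0 |
| 7-day holiday, then 600 mg | 21 × 0.6 = 12.6 g | 4.2 g |
| 400 mg daily | 28 × 0.4 = 11.2 g | 5.6 g |
| 7-day holiday, then 400 mg | 21 × 0.4 = 8.4 g | 8.4 g |
| 14-day holiday, then 400 mg | 14 × 0.4 = 5.6 g | 11.2 g |

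**6. How many people?** The documents give no frequency. As an illustration only, assume that 0.5% to 3% of 100 HCQ recipients exceed 500 ms and that 10% to 50% of those have a second cause. The expected number is 100 × 0.005 × 0.10 = 0.05 to 100 × 0.03 × 0.50 = 1.5. The chance of at least one is 1 − (1 − 0.0005)^100 = 4.9% to 1 − (1 − 0.015)^100 = 77.9%. This is an upper bound because it counts every such person, including those for whom staff simply follow 8.4.2. The range is too wide to support a numerical claim.

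**The case against.** The best reply is that 8.4.2 is the specific rule for exactly this reading and 8.5 is the general rule that supplies the dose steps. One section requires an action and the other is silent, so they do not contradict each other. The word *possibly* also softens *solely*: if HCQ alone might explain the prolongation, the condition can be met even with a second drug present.

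Much of this stands. A reader might infer that 8.5 forbids a reduction or that staff cannot comply with both sections. The documents do not support that, because reducing the dose satisfies both. A reader might also infer that such a participant would be left on full dose. That does not follow either, since other routes exist:

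- Section 8.2 delays drug for unrelated grade 3 or 4 events that HCQ may complicate.
- Section 8.5 itself holds drug for any adverse event of grade 3 or higher.
- Section 10.3 lets the investigator discontinue participation for any reason.

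These routes do not fully close the gap. The first two depend on a CTCAE grade that the documents do not give for QTc. They also depend on the reading counting as an adverse event, which section 11.0 grants only under listed conditions (a value above 500 ms would often qualify as clinically significant). The third is discretionary. The view that 8.4.2 alone governs is plausible, but the protocol does not state it.

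**Conclusion.** The point holds as a minor inconsistency in a safety rule. On its natural reading, 8.5 requires action on QTc above 500 ms only with an attribution that 8.4.2 does not mention and that blinded staff cannot readily judge. Whether 8.4.2 takes on that condition is left open.

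The documents do not give the number of participants affected, and it may be zero. For any one of them, the dose difference over the last four weeks would be 4.2 to 11.2 g. That assumes the holiday lengths above and that no one acted under 8.4.2 or the other routes. The sample size and the planned analyses are untouched.

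One might also conclude that *solely* should be removed from the adverse event trigger. The QTc mismatch gives no support for that; it is a separate and debatable change.

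**What to change.** In 8.5, separate the QTc trigger from the attribution clause, for example: *Adjusted QTc >500 ms, whatever the suspected cause, will result in a dose holiday and/or dose reduction of blinded study drug.* This agrees with 8.4.1 and 8.4.2. Leave the grade 2 or higher adverse event trigger unchanged.

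The cost is one sentence. The downside is possibly a few more dose changes, some in placebo recipients and some in participants whose long QTc has another cause.

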9.0 SCHEDULE OF EVENTS

Table 4. Schedule of events for sub-study 1			
	Before treatment	During treatment	Day of release from quarantine
Eligibility checklist	X		
Temperature (patient obtained)		Twice daily	X
COVID-19 symptom score		Daily	
Mobile Cardiac Telemetry	X	Daily	X
AE assessment, triage		Daily as needed	X
SARS-COV-2 PCR nasopharyngeal swab	X		
SARS-COV-2 PCR nares swab ¹	X	D3, D7	X (if ≤7 or 10 days, per CDC guidelines)
Oral fluid collection ²	X	D3, 7	X
TREATMENT			
Hydroxychloroquine or placebo		Twice every day	Return electronic diary

1- The nares swab before treatment sample can be performed at any time of day and should be collected before any study medication has been taken.

The PATCH Trial

2-For oral fluid collections, these should be performed in the morning to maintain consistency. For the before treatment collection, if HCQ is received during the day, there should not be a delay in starting HCQ in order to collect morning oral fluid. Instead study medication should be started and the next morning the first sample can be collected and considered the baseline sample. The timing of collection should be recorded in the daily diary.

Table 6. Schedule of events for Sub-study 3			
	Baseline / Pre-RX	During 2 months	End of 2 months
Eligibility checklist	X		
COVID-19 symptom score	X	Weekly	
AE check by telephone		1X/week	X
PCR SARS-COV-2 ¹	X	One month	X ²
Oral fluid collection	X	Every 2 weeks	X
Research Blood ²	X	One month	X
6 or 12 Lead Electrocardiogram	X	One month	
TREATMENT			
Hydroxychloroquine or placebo		3 pills daily	

- 1- this testing is dependent on availability of the test kits and can be deferred if test kits or testing capacity are not available
- 2- End of 2 months or at the time of symptom progression 3- one 10-mL tiger top serum separator tubes (SST). This collection can be deferred to accommodate the conditions of the COVID-19 crisis situation and how it affects resources and health care worker schedules.
- 3- If subject has had an EKG in the last 6 months the baseline EKG can be deferred. Since this EKG is for research purposes only, the serial EKGs can be deferred to accommodate the conditions of the COVID-19 crisis and how it affects resources and health care worker schedules.

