4.1.2 Sub-Study 3 Outpatient Hospital Workers

1. Healthcare workers will enroll in stations in the ED.
2. Delegated and credentialed clinical investigator sends consent via email/DocuSign and reviews consent form with the participant
3. Conducts e-consent process with the patient and documents via telemedicine/DocuSign
4. If a participant is a member of the PATCH study team, then they are counselled to ensure they do not reveal their own participation during the consenting of participants to Sub-study 1.
5. Eligibility checklist is reviewed and signed by an appropriately delegated and credentialed clinical investigator

The PATCH Trial

6. Participant is randomized by IDS
7. Sub-Investigator orders study drug and PCR test.
8. Nasopharyngeal swab for COVID19, and blood collection if available/possible is performed in the designated area
9. A baseline ECG (6 lead ECG is acceptable) will be obtained if the participant has not had one recently. If the participant has had an ECG in the last 6 months, and they have not started any QT prolonging medications in the interim, the previously obtained ECG can be used.
10. Blinded study drug and 5 oral fluid collection kits are provided to the participant by Study member who reviews dosing of study drug (three pills daily) with the participant.

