5.0 RANDOMIZATION

After all applicable screening assessments have been performed, participants who have met all inclusion criteria and none of the exclusion criteria will be centrally, randomly allocated to one of the two groups in each sub-study. Randomization will be done using computer generated randomization numbers. Treatment **should start within 3 working days after randomization.** Once the order for study drug arrives at the

The PATCH Trial

pharmacy and the participant is randomized only the pharmacist is aware of the assignment of HCQ versus placebo in the double blind sub-studies (1 and 3).

Blinding: Sub-Study 1 and 3 will have a double-blind placebo controlled design.

Unblinding: Sub-Study1: If a participant progresses with symptoms of COVID-19 based on the assessment scale outlined below an appropriately delegated and credentialed study team member will review the case with a clinical investigator who will sign off on the need to un-blind the participant. If the participant was on placebo and continues to have symptoms, then he/she will be allowed to crossover to the HCQ dosing. The EM van will deliver the HCQ to the participant. If the patient was on HCQ then HCQ will be stopped and the patient will be asked to seek the advice of their primary care doctor or go to the emergency room if symptoms are becoming more worrisome. Participants who have progressive symptoms and are subsequently hospitalized due to COVID-19 will be unblinded but not be crossed over to receive HCQ at the time of unblinding.

Sub-Study 3: If the participant at any time has worsening symptoms consistent with new onset of COVID-19 disease a COVID-19 PCR test is performed. Antibody tests alone will not be used to make decisions for this study. If the PCR test is positive for SARS-CoV-2 an appropriately delegated and credentialed study team member will contact IDS and the pharmacist will indicate which arm the participant was assigned. If the participant was assigned to placebo and wishes to cross over to HCQ, IDS will provide HCQ at the same dose as the Sub-Study 3 HCQ arm and IDS will ship the HCQ to the participant. If the participant was assigned to HCQ then the participant will be advised to seek the advice of their personal physician or go to the emergency room if symptoms are becoming more worrisome.

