3. Live attenuated vaccines during the study
4. Herbal and natural remedies must be avoided

7.4 Duration of Protocol Treatment and Follow-up.

Sub-Study 1 duration of treatment is up to 2 weeks or at the time of release from quarantine. HCQ will be stopped in all patients at the time of release from quarantine

Sub-Study 3 duration of treatment is 2 months with assay to assess SARS CoV2 every 2 weeks.

7.5 Crossover from Control to HCQ arm. For Sub-Study 1 all participants are un-blinded upon symptom progression (see response assessment below) after at least 7 days of treatment or upon hospitalization if this occurs prior to 7 days of treatment. If the participant was assigned to placebo, he/she has the option to crossover to receive HCQ 400 mg po bid for up to 2 weeks or until criteria for release from quarantine are met (See 1.0 primary endpoint). During these 2 weeks of HCQ treatment, the patient will continue to complete the daily diary. An appropriately delegated study team member will call the patient daily to assess worsening symptoms and AEs. Patients who are not improving will be sent to the hospital for further care. Participants who have progressive symptoms and are subsequently hospitalized as related to COVID-19 will not be crossed over to receive HCQ at the time of unblinding.

In sub-study 3 participants who have worsening symptoms as defined as fever, significantly worsening cough, shortness of breath or hypoxia but do not require hospitalization and tests positive for SARS-CoV2 virus are allowed to cross over to receive HCQ, or treated with an alternative therapy per physician's choice. Once the positive test returns, the CRC will email IDS to initiate unblinding IDS will inform the CRC and clinical investigator if the patient was on placebo. The clinical investigator will contact the subject and inform them that if they were on placebo they would have the option of being treated with HCQ 600 mg qd. If the patient agrees, the clinical investigator will place the order in EPIC for HCQ 600 mg qd through IDS. Drug will be delivered to the patient's home. During these 2 weeks of HCQ 600 mg po qd treatment, clinical investigators will call the patient every 1-3 days depending on the severity of symptoms to assess worsening symptoms and AEs. Patients who are not improving will be sent to the hospital for further care.

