Anterior nares specimen: Participants will self-collect these samples on day 0 (start date for HCQ) before the HCQ is taken, Day 3, and day 7

The PATCH Trial

Foam swab provided: Puritan 6" Sterile Standard Foam Swab w/ Polystyrene Handle (SKU # 25-1506 1PF)

Collection instructions: Use a single foam swab for collecting specimens from both nares. Insert foam swab into 1 nostril straight back (not upwards). Once the swab is in place, rotate it in a circular motion 2 times and keep it in place for 15 seconds. Repeat this step for the second nostril using the same swab. Remove foam swab and insert the swab into the supplied tube.

Storage instructions: The collected swab should be placed into the bag marked "Nares swabs collected" and the date and time of the swab collection should be filled out Redcap. The "Collected" bag is then placed in the freezer in the same sealed container as the oral fluid.

Specimen stability for all specimen types for all tests is now as follows:

Room temperature: 5 days

Refrigerated (2 °C–8 °C): 5 days

Frozen (-20 °C): 7 days

Frozen (-70 °C): Acceptable

Specimen pickup: At the end of quarantine, or end of study procedures, the nares swabs will be collected. And shipped to Quest Diagnostics to assess viral titers. Cold packs or dry ice should be used during collection and cold packs should be used during shipping to Quest.

Pill diary: When the participant is released from quarantine the electronic pill diary must be submitted electronically.

Monitoring co-inhabitants: Appropriately delegated and credentialed study team members (as example: Clinical Research Coordinator) will ask the participant about the status of co-inhabitants daily to 14 days after the quarantine is completed to determine if the participant's co-inhabitants did or did not have symptoms or tested positive for COVID-19.

8.4.2 Sub-Study 3:

SARS-CoV-2 testing: Hospital workers will be tested for SARS-CoV-2 virus by RT-PCR every month. This will be a nasopharyngeal swab that will be processed by Quest diagnostics performed during enrollment at one month and two months. This screening NP swab will provide results in EPIC for clinical action within 72 hours. Eligibility criteria to start study medication does not require a negative PCR result to return.

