Asymptomatic PCR+ at baseline: Given the 20% prevalence of asymptomatic coronavirus infection, we will need to screen 250 subjects to accrue the target enrollment of 200 to address the primary endpoint. If the PCR test returns positive while the health care worker is enrolled on the study, the participant will be notified and offered to be removed from the study or to continue with the study medication. Baseline PCR+ subjects who decide to withdraw from the study will be asked to go to occupational health and seek the care of their primary physician. Their study medication will remain blinded and the subject will be asked not to take any additional study medication. For baseline PCR+ subjects who decide to continue on study, they will be asked to keep the daily pill diary. If these subjects are asymptomatic after one week of study medication, they will be asked to return to undergo an on treatment nasopharyngeal swab. If the subject develops symptoms on study medication after 7 days of treatment, the subject will be unblinded. If the subject was assigned to placebo, they will have the option to crossover and get treatment with HCQ 600 mg qd for up to 7 days. Weekly phone calls per the sub-study 3 schedule will continue during this time. AEs will be reported as planned for the study. Baseline PCR+ subjects will be replaced in the prevention study related to the primary objective of sub-study 3 and will not count towards the target accrual or interim analysis. Baseline PCR negative subjects who screen positive at the one month or two-month mark will be considered COVID-19 positive as it relates to the primary endpoint.

Asymptomatic PCR+ at one month: These subjects will count towards the primary endpoint of sub-study 3 as an infection event. Accordingly, they will be unblinded and if on placebo they will be allowed to crossover to HCQ 600 mg qd for 2 weeks. If the subject is assigned to HCQ and turns PCR positive while asymptomatic, the subject will be stopped from study drug and referred to occupational health for standard of care management of health care worker infection. Weekly phone calls will continue. If the subject remains asymptomatic after one month, he/she will return for the one-month swab.

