10.0 MEASUREMENT OF EFFECT

10.1 Definitions

Evaluable for toxicity. All participants will be evaluable for toxicity from the time of their first treatment with HCQ or placebo.

Evaluable for primary outcome: Participants who received at least one dose of study drug will be evaluable for the primary outcome as long as they meet the following status for SARS-COV2 PCR: sub-study 1: PCR+ Sub-study 3: PCR negative.

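### Sub-Study 3 lets the baseline PCR swab be deferred without tying it to the first dose, so a swab taken on treatment could turn an infection event into a baseline exclusion

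*Protocol*

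**What the plan says.** **Baseline PCR governs the primary analysis.** Protocol 10.1 makes participants evaluable for the primary outcome after one dose "as long as they meet the following status for SARS-COV2 PCR: sub-study 1: PCR+ Sub-study 3: PCR negative". Protocol 8.4.2 adds that "Baseline PCR+ subjects will be replaced in the prevention study" and leaves them out of target accrual and the interim analysis. The SAP table of analysis sets likewise requires a negative status at baseline.

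**The baseline swab may be deferred.** In the current Table 6 (Protocol 9.0), footnote 1 hangs on the label of the PCR row, which spans the baseline, one-month and two-month columns. It reads: "this testing is dependent on availability of the test kits and can be deferred if test kits or testing capacity are not available". It sets no limit on the delay.

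**Drug start is not linked to the swab.** Protocol 5.0 expects treatment within 3 working days of randomization. Protocol 8.4.2 states: "Eligibility criteria to start study medication does not require a negative PCR result to return".

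**Other text implies a pre-dose swab.** Protocol 4.1.2 places the swab at step 8 and hand-over of drug at step 10. The Table 6 column is headed as baseline and pre-treatment. The SAP, under Study Design, has every subject swabbed at baseline, 4 weeks and 8 weeks.

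**Two further timings differ.** Table 6 footnote 2 sets the last swab at "End of 2 months or at the time of symptom progression". Protocol 7.4 says: "Sub-Study 3 duration of treatment is 2 months with assay to assess SARS CoV2 every 2 weeks".

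**The concern.** Baseline status should be fixed before treatment can influence it. If a first swab taken on treatment counts as baseline, it becomes a post-randomization measurement that depends on the outcome. A participant infected between the first dose and that swab leaves the numerator and the denominator and is replaced. If the drug works, most of the infections removed in this way come from placebo, and the contrast shrinks.

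The footnote looks like text that was not updated. The original protocol carries the same footnote, and its section 8.5.3 said the assay was not required for participation. Testing at enrolment is now firm, and since Amendment 4 the baseline result decides evaluability, but the permission to defer was left as it stood.

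The other two timings affect how the endpoint is ascertained. If a negative swab at the time of symptoms stood in for the 8-week swab, a later infection could be missed, and the SAP does not impute missing values.

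**Working it through.** **Step 1: the passages side by side.**

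| Question | Text allowing a late first swab | Text against |
|---|---|---|
| May the baseline swab wait? | Table 6 footnote 1, on the whole row, no limit | Pre-treatment column header; 8.4.2 places a swab at enrolment; SAP Study Design |
| Must the swab precede the drug? | No sentence for Sub-Study 3; start within 3 working days (5.0); no negative result needed (8.4.2) | 4.1.2: swab at step 8, drug at step 10 |
| Can a post-dose sample be baseline? | Not defined for Sub-Study 3 PCR | 8.4.2 treats a one-week swab as on-treatment |

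Sub-Study 1 (Table 4 footnotes) settles both matters for its own samples. Its pre-treatment nares swab must come before any study medication, while an oral fluid sample taken the morning after dosing may serve as baseline. Sub-Study 3 PCR has neither sentence.

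**Step 2: the plan's own figures.**
- Screening number (8.4.2), with 20% baseline positive: 200 / (1 − 0.20) = 250. Reproduced.
- Power (13.1), with 10% v 1%, 100 per arm and one-sided 0.05. The pooled standard error is √(0.055 × 0.945 × 2/100) = 0.0322 and the unpooled one is √((0.09 + 0.0099)/100) = 0.0316. With a continuity correction of 1/100, Φ((0.09 − 0.01 − 1.6449 × 0.0322)/0.0316) = 80.3%, which matches the 80% in 13.1. The same section (interim analysis) and the SAP also state 84%.

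**Step 3: infections moved from event to exclusion.** Assume a constant hazard over 8 weeks and a first swab w weeks after the first dose. The fraction infected by then is 1 − (1 − p)^(w/8). Per 100 deferred participants:

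| w | Placebo (p = 0.10) | HCQ (p = 0.01) |
|---|---|---|
| 1 week | 1.3 | 0.13 |
| 2 weeks | 2.6 | 0.25 |
| 4 weeks | 5.1 | 0.50 |

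**Step 4: effect on power.** For those who stay in, the remaining risk is 1 − (1 − p)^(1 − w/8). At 2 weeks this is 1 − 0.9^0.75 = 7.60% on placebo and 1 − 0.99^0.75 = 0.75% on HCQ. If a share q of analysed participants had a deferred swab, the arm rate is (1 − q)p + q × (remaining risk). Power is the exact binomial probability that the pooled z reaches the plan's final critical value, 1.6664, with 100 per arm and a single look.

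| Share deferred 2 weeks | Placebo | HCQ | Power |
|---|---|---|---|
| 0% | 10.00% | 1.00% | 92.6% |
| 10% | 9.76% | 0.98% | 91.9% |
| 25% | 9.40% | 0.94% | 90.9% |
| 100% | 7.60% | 0.75% | 83.9% |

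With every swab deferred, 1 week gives 89.0% and 4 weeks gives 68.4%. The 92.6% reference is above the plan's 80% and 84% because it is an exact single-look figure. Only the differences within the table matter here.

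**Step 5: why a late first positive cannot simply be counted.** At the plan's 20% prevalence, 100 participants include about 20 already infected at the first dose. Two weeks on placebo adds about 80 × 0.026 = 2.1 new infections. A single late positive cannot separate the two groups, so the rule has to be set in advance.

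**The case against.** The strongest reply is that the mechanism is inferred. No sentence tells a site to dose before swabbing or to enter an on-treatment swab as baseline. The normal order is swab then drug, and waiving the wait for a result presupposes that a swab was taken. The footnote to the ECG row names the baseline ECG as deferrable, while the PCR footnote does not name the baseline swab. All of that stands, and it makes this a conflict between passages. It does not remove the conflict, because footnote 1 is attached to a row that includes the baseline cell.

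Four stronger readings are tempting, and the documents do not support them.
- A reader might infer that randomizing before the swab breaches section 5.0, which begins "After all applicable screening assessments have been performed, participants who have met all inclusion criteria", because "Participant is randomized by IDS" is step 6 of 4.1.2. A negative PCR is not a Sub-Study 3 inclusion criterion (3.1), and 8.4.2 says so. A swab after randomization but before the first dose cannot be affected by treatment.
- A reader might infer that early testing prompted by gastrointestinal side effects would favour HCQ. The overlap of diarrhea and nausea with COVID-19 is described for Sub-Study 1 only. The Sub-Study 3 symptoms in 7.5 and 10.3 are fever, cough, shortness of breath and hypoxia.
- A reader might scale the full-deferral loss by the share deferred. At 2 weeks the full loss is 92.6 − 83.9 = 8.7 points, and a quarter of that is 2.2. The computed loss at 25% is 92.6 − 90.9 = 1.7.
- A reader might infer type I error inflation. With no drug effect, the exclusions are expected to fall equally on two blinded arms.

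On footnote 2, Protocol 10.3 ties Sub-Study 3 progression to a positive test. On that reading only a positive swab, already an event, replaces the last one. The two-weekly assay in 7.4 may mean the oral fluid samples, which are collected every 2 weeks. Both are reasons to clarify the text, and neither is evidence of harm.

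**Conclusion.** The point holds as a gap that should be fixed. A written permission to defer covers the baseline swab, baseline has no window, and baseline status controls membership of the primary analysis. Together these allow an outcome-dependent exclusion after randomization. The expected harm is lost events and some lost power.

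The size rests on assumptions that the documents do not supply: how often and how long swabs are deferred, a constant hazard, and the planned 10% v 1%. If 10% to 25% of swabs are deferred 2 weeks, the loss is about 1 to 2 points of power. If all are, it is about 9 points. The 4-week, all-deferred case is an outer bound, since that swab would coincide with the scheduled one-month swab. The case for changing the text rests on keeping the analysis set free of post-treatment information, at little cost, more than on the power figures.

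**What to change.** 1. Reconcile Table 6 footnote 1 with 4.1.2, the pre-treatment column and the SAP, so that the deferral does not apply to the baseline swab.
2. In Protocol 10.1 and the SAP analysis-set table, define baseline PCR as a swab collected before the first dose.
3. State that a first swab taken after dosing cannot by itself make a participant baseline positive and replaced. Set one rule in advance for participants with no pre-dose swab, applied whatever their later results, and add a sensitivity analysis that handles them the other way.
4. Reconcile footnote 2 with the SAP, so that a negative swab at the time of symptoms does not replace the 8-week swab.
5. Reconcile the two-weekly assay in 7.4 with the baseline, 4-week and 8-week PCR schedule, or state that it refers to oral fluid.

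The cost is a wording amendment to Table 6, 7.4, 10.1 and the SAP, plus one sensitivity analysis. In a kit shortage some enrolments would wait for a swab, and a few participants would have both a symptom-time and an 8-week swab.
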